4.4.1.2. Strategy 2: Missing ANC values not imputed, censored handling unresolved SN

For patients who experienced at least 1 episode of severe neutropenia (SN) within each cycle, a DSN is defined as the number of days from the date of the first absolute neutrophil count (ANC) value $< 0.5 \times 10^{9}$ /L in that cycle to the date of the first ANC value $\ge 0.5 \times 10^{9}$ /L that meet the following requirements: (1) occurred after an ANC value $< 0.5 \times 10^{9}$ /L, and (2) no other ANC value $< 0.5 \times 10^{9}$ /L occurred between that date and the end of that cycle (otherwise the SN event is considered not resolved at the end of that cycle). Patients will not be included in the analysis if they does not experience any SN during this period. Exceptions will be handled using the following rules:

- If the SN event is not resolved at the end of the cycle, the DSN will be calculated as described above, but the end date will be the end date of the cycle or the last contact date, whichever occurs first;
- If a patient dies, withdraws consent, or is lost to follow-up during the period of the SN event, the DSN will be calculated as described above, but the end date will be the last ANC assessment before the end of the study.

Overall DSN (days) during treatment is the median DSN value for all cycles and the following data handling rules will be applied:

- If a patient 's SN event duration value is censored for all cycles, the patient' s median DSN value will be the median censored value and will be considered censored;
- If a patient 's partial cycle SN time duration value is a censored value, the Kaplan-Meier method will be used to estimate the median DSN value for that patient, which is the observed value;
- ➤ If a patient 's median DSN value cannot be calculated (eg, has ≤ 2 DSN values), the longest DSN value across all cycles (whether censored or not) will be used as the median value, but the corresponding censoring flag will be included in the analysis.

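### Strategy 2 scores a patient with exactly two unequal DSN values by the longer one, and a patient with three or more by the median, so overall DSN mixes two statistics

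*SAP*

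**What the plan says.** SAP 4.4.1.2 sets the target quantity: "Overall DSN (days) during treatment is the median DSN value for all cycles". Three handling rules follow.

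- **All values censored:** the patient's "median DSN value will be the median censored value and will be considered censored". No minimum number of values is given.
- **Some values censored:** "the Kaplan-Meier method will be used to estimate the median DSN value for that patient, which is the observed value".
- **Median not obtainable:** the trigger is that the patient's "median DSN value cannot be calculated (eg, has ≤ 2 DSN values"), and then "the longest DSN value across all cycles (whether censored or not) will be used as the median value". Whether that substitute counts as observed or censored follows its own status: "but the corresponding censoring flag will be included in the analysis".

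Patients without SN are left out of Strategy 2: "Patients will not be included in the analysis if they does not experience any SN during this period". The same section then specifies Kaplan-Meier quartiles, a stratified Cox hazard ratio and a stratified log-rank test for the duration of SN. SAP 4.4.1 labels Strategy 2 supportive, and SAP 4.9 uses it to check the stability of the Cycle 1 result. Nothing elsewhere in the SAP or protocol explains or overrides the third rule.

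**The concern.** The reason given for the fallback is incorrect when nothing is censored. The median of one value is that value, and the median of two is their mean. With one value the fallback does no harm, because maximum and median coincide. With two unequal values it enters the maximum and calls it a median. With three or more values the plan returns to the median. The summary statistic therefore depends on how many SN cycles a patient had.

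That number arises after randomisation, and treatment is expected to change it. Protocol Table 3 gives SN in 52.9% of placebo and 11.4% of trilaciclib patients in the integrated analysis. A score whose definition switches with that number can produce a difference between arms when individual episodes last equally long in both.

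**Working it through.** The plan states no figure for this rule, so there is none to reproduce. The check applies the rule as written.

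**Reading used.** DSN values come only from cycles with SN. The exclusion of patients without SN supports this, but the SAP does not say it for single cycles.

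**1. Uncensored examples.** Rule: maximum if there are at most two values, otherwise the median.

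| DSN values (days) | Ordinary median | Score under the rule |
|---|---|---|
| 5 | 5 | 5 |
| 4, 10 | (4 + 10)/2 = 7 | 10 |
| 2, 9 | (2 + 9)/2 = 5.5 | 9 |
| 4, 10, 4 | 4 | 4 |

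A third, short SN cycle lowers the score from 10 to 4, so a patient with more severe neutropenia ranks better.

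**2. Size for one patient.** Assumption, not from the documents: durations follow a gamma distribution (shape 2.2, mean 7 days) rounded to whole days, identical and independent in every SN cycle. Simulated mean scores:

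| SN cycles | Under the rule | Ordinary median |
|---|---|---|
| 1 | 7.0 | 7.0 |
| 2 | 9.5 | 7.0 |
| 3 | 6.4 | 6.4 |
| 4 | 6.4 | 6.4 |

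The excess at two cycles is 9.5 − 7.0 = 2.5 days, or 2.5/7.0 = 36%. With other assumed distributions (mean 5 to 8 days, SD 2 to 4) it is about 1.1 to 2.2 days.

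**3. Effect between arms.** The same durations were used in both arms, with 4,000 simulated patients per arm and a proportional-hazards fit for resolution. A hazard ratio below 1 means longer scores on trilaciclib. The documents do not give the distribution of SN cycles per patient, so both mixes are assumed.

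| Patients with 1/2/3/4 SN cycles, trilaciclib vs placebo (%) | HR under the rule | HR with ordinary median |
|---|---|---|
| 50/40/10/0 vs 30/20/25/25 | 0.84 | 0.93 |
| 80/15/5/0 vs 40/35/15/10 | 1.05 | 0.94 |

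Repeat runs moved these by a few hundredths: 0.81 to 0.85 against 0.89 to 0.93 for the first mix, and 1.05 to 1.09 against 0.94 to 0.98 for the second. Trilaciclib has fewer SN cycles in both mixes, yet the rule shifts the ratio down in one and up in the other. What differs is the share with exactly two cycles: 40% vs 20% in the first mix and 15% vs 35% in the second.

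**4. Overlap of the rules when values are censored** (+ marks a censored value; the Kaplan-Meier median is taken as the first time survival is at or below 0.5).

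- 4+ and 10+: the all-censored rule gives (4 + 10)/2 = 7, censored. The fallback gives 10, censored.
- 4 and 10+: the Kaplan-Meier rule gives 4, observed. The fallback gives 10, censored.
- 4+ and 10: both rules give 10, observed, so there is no conflict.
- 4, 7+ and 10+: the Kaplan-Meier median is not reached, so the fallback properly applies.

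The SAP states no precedence, so two programmers could build different datasets from the first two cases.

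**5. Reach.** If the integrated rates in Protocol Table 3 held with about 40 patients per arm, 40 × 0.114 = 4.6 trilaciclib and 40 × 0.529 = 21.2 placebo patients would enter Strategy 2. Those with exactly two unequal values are a fraction of these.

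**The case against.** The strongest counter-argument is that little depends on this. Strategy 2 is supportive. SAP 4.9 uses it to check Cycle 1 DSN, and Cycle 1 gives one value per patient, so the fallback cannot alter that check. Overall DSN across cycles is not in the endpoint list of Protocol 2.2. Few patients are likely to enter, and large simulated arms say little about a comparison with about five trilaciclib patients. All of this stands, and it keeps the point minor.

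The fallback also has a proper use. Where censoring leaves the within-patient Kaplan-Meier median unreached, the longest value with its flag is a workable choice. The objection here is only to the trigger at two or fewer values.

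A reader might go further and infer that the rule works against trilaciclib, because fewer SN cycles would move its patients into the group scored by the maximum. The documents do not support that. Fewer cycles can equally move patients from two to one, where maximum and median agree. The second mix above shows a shift in trilaciclib's favour.

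Nor is the rule the only source of a ratio different from 1. The ordinary median also gives about 0.93, since the distribution of a median depends on how many values it summarises.

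**Conclusion.** The rule is wrong as written, with limited consequences. It misstates when a median exists, and it scores patients with exactly two unequal uncensored values by their maximum. Under identical episode lengths with an assumed mean of 7 days, that adds about 2.5 days to such a patient's score. The examples with 4 and 10 days need no assumption beyond the reading that DSN values come from SN cycles.

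The overall-DSN quantiles, hazard ratio and log-rank test can be distorted because treatment is expected to change the number of SN cycles. The size and sign depend on the number of patients per arm with exactly two SN cycles, which the documents do not give. Separately, the three handling rules conflict for two values when the longer is censored. Cycle 1 DSN, Strategy 1 and the sample size are untouched.

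**What to change.** Amend SAP 4.4.1.2 before unblinding, as follows.

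1. With no censored values, use the ordinary median for any number of SN cycles: the value itself for one, and the mean of the two for two.
2. Reserve the longest value, with its censoring flag, for patients whose within-patient Kaplan-Meier median is not reached because of censoring.
3. State the order in which the three rules apply, and say explicitly which governs two values when one or both are censored.
4. Confirm that cycles without SN contribute no DSN value in Strategy 2.

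The cost is a few sentences of SAP text and a small change to the derivation code. No new data are needed, and no other analysis changes.

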4.4.2. Key Secondary Efficacy Endpoints

Key secondary efficacy endpoints include the incidence of severe neutropenia (SN), the incidence of red blood cell (RBC) transfusions (occured on/after Week 5), granulocyte colony-stimulating factor (G-CSF) use, and the composite endpoint of major adverse hematologic event (MAHE).

4.4.2.1. Incidence of serious neutropenia events

The total number of SN events is the total number of cycles with at least one ANC value $< 0.5 \times 10^{9}$ /L. For example, two ANC values less than 0.5 x 10⁹/L during Cycle 2 are counted as only one SN event. If a patient does not experience any SN events, the number of SN events for that patient will be counted as zero. Unscheduled data will be included and and actual SN assessment date (non-visit date) will be used. Whether a patient experienced a SN event is a binary variable (yes or no); 'yes' if ≥ 1 cycles with a SN event is observed; and 'no' otherwise.

SN events will be summarized by treatment group using descriptive statistics. Part 2 of the study will analyze the adjusted rate ratio (aRR) between the two treatment groups based on a modified Poisson regression model. The model includes baseline ANC measurement as covariate and IRT-based randomization stratification factors including number of lines of therapy (1st line versus 2nd/3rd line), ECOG (lines 0-1 versus 2) (not included in the actual analysis), and brain metastases (yes versus no), as well as treatment arm as fixed effects. Logarithmic transformed values of the number of cycles will be included in the modeling as offset variables. P-values, aRR (Trilaciclib versus placebo) and their 95% CIs will be provided for the 2-sided tests. In addition, Cochran-Mantel-Haenszel (CMH) weights will be used to calculate the adjusted rate difference between the two arms (Trilaciclib versus placebo) and its 95% CI in Part 2 of the study, and stratified exact CMH method will be used to calculate P values under the 2-sided test according to IRT-based randomization stratification factors to test the stability of the analysis results.

4.4.2.2. Incidence of red blood cell transfusion events occured on/after Week 5

Each red blood cell (RBC) transfusion (including whole blood transfusion and each red blood cell component) occured on/after Week 5 is defined as a separate event and included in the efficacy analysis. Whether a patient experiences a RBC transfusion event is defined as a binary variable (yes or no); "yes" if a total number of RBC transfusion events ≥ 1 is observed, otherwise "no".

The statistical analysis method is similar to that described for SN incidence in Section 4.4.2.1, except hemoglobin (HGB) baseline measurement will be used as covariate instead of

ANC baseline measurement in a modified Poisson regression model. In addition, the offset variables will be log-transformed values for duration of treatment (weeks) rather than cycles.

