4.4.2.3. Use rate of granulocyte colony-stimulating factor

Prophylactic use of any prophylactic colony-stimulating factors (including granulocyte colony-stimulating factor G-CSF, granulocyte-giant cell colony-stimulating factor, erythropoietin) is not permitted in principle in Cycle 1, but febrile neutropenia with high-risk infections or risk factors suggestive of poor prognosis is permitted for therapeutic use.

Determine if G-CSF is used in this cycle by comparing the start and end dates of each use of granulocyte colony-stimulating factor (G-CSF) with the start and end dates of the treatment cycle. If the date of G-CSF use lies between the start and end dates of the cycle, the cycle will be considered as having G-CSF use. The total number of events with G-CSF use is the total number of cycles with at least one GCSF administration. If a patient does not take any G-CSF, the number of G-CSF administration events for that patient is zero. Thus, whether a patient experiences an event of G-CSF administration is defined as a binary variable (yes or no); "yes" if the number of cycles with G-CSF administration is ≥ 1 and "no" otherwise.

Statistical analysis method is similar to that for SN incidence described in Section 4.4.2.1.

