4.4.2.4. Total occurrence of major adverse hematologic event

Major adverse hematologic event (MAHEs) are composite endpoints to assess the effect of Trilaciclib. MAHE consists of the following 5 component events:

- Involved hospitalization
- Leading to chemotherapy dose reduction
- Febrile neutropenia
- Extended SN (greater than 5 days)
- RBC transfusion occured on/after Week 5.

The total number of events for each MAHE component is the sum of the number of events that occurred on the date of first study drug administration and before the end of the last treatment cycle. The total number of events for MAHEs during treatment is the sum of the number of events for each MAHE component. For patients who does not experience any MAHE, the total number of MAHE events is 0.

MAHEs will be coded using the most current version of MedDRA and the total number of MAHEs, duration of treatment (weeks), weekly event rates, and cumulative event rates every 3 weeks will be summarized by number of lines of treatment. According to the actual MAHEs, the above summaries will be repeated separately by component events , but for MAHE component events leading to chemotherapy dose reduction and SN prolongation, the cumulative

event rates will be summarized by cycle rather than every 3 weeks. Part 2 of the study will also analyze the adjusted rate ratio between the Trilaciclib and placebo groups using a negative binomial regression model. The model includes the three IRT-based randomization stratification factors and treatment group as fixed effects, and the log-transformed values of treatment duration (weeks) or cycle number as offset variables. Two-sided P values, aRR (Trilaciclib versus placebo) and their 95% CIs will be provided. Cumulative incidence of MAHEs within specified subgroups will be presented using forest plots.

Time to first onset (months) for each MAHE component event = (date of first MAHE component event – date of first study drug administration + 1)/30.

For patients who developes MAHEs, the time (months) from the first study drug administration (randomization date in Part II) to the first occurrence of MAHEs will be summarized and Kaplan-Meier curves will be provided. Time to first MAHE refers to the event with the shortest time to first occurrence of the MAHE component; if a patient does not have an MAHE, it will be censored at the end date of the last cycle, date of death, end of study, or last contact date for that patient, whichever cames first.

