4.4.3.3. Other dichotomous endpoints

The total number of events below is the total number of cycles with at least one event. If a patient does not experience any of the following events during the treatment period, the number of events for that patient is zero. 'Yes' if ≥ 1 of the following events are observed; otherwise 'No'.

- Incidence of Grade 3 and 4 Hematologic Toxicities: Grade 3 and 4 hematologic toxicities refers to hematology laboratory results with CTCAE Grade 3 or 4.
- Incidence of platelet transfusion (during chemotherapy)
- Incidence of febrile neutropenia

Each of the following events with a unique start date will be defined as a separate event during the treatment period. Yes if the total number of the following events observed is ≥ 1 , otherwise no.

- Incidence of intravenous or oral antibiotics
- Incidence of infectious serious adverse events
- Incidence of serious adverse events of lung infection

Determine if the following medications is used in that cycle by comparing the start and end dates of each use of the following medications with the start and end dates of the treatment cycle. The total number of events with the following medications is the total number of cycles with at least one dose of the following medication. If a patient did not take the following medications during the treatment period, the number of events for that patient is 0.

- Erythropoiesis-stimulating agent (ESA) Usage
- Recombinant human interleukin-11 (IL-11) use rate
- Thrombopoietin (TPO) use

The total number of events as well as the incidence of the above dichotomous variables will be summarized descriptively and tabulated in detail by patient. The statistical analysis approach is similar to that described for SN incidence in Section 4.4.2.1, except that baseline ANC measurements will not be included as covariates in the modified Poisson regression model.

In addition, for comparing the incidence of antibiotic administration, SAEs of infection, and SAEs of lung infection between the Trialciclib and placebo groups, the offset variable in the modified Poisson regression model will be the log transformed duration of treatment (weeks) rather than the number of cycles.

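### The modified Poisson model for yes/no endpoints appears to carry an exposure offset that does not fit a capped outcome; the SAP should name the response and match it to the offset

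*SAP*

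**What the plan says.** SAP 4.4.2.1 derives two SN variables per patient: the number of cycles with at least one ANC value below the threshold, and an indicator. Of the indicator it says "Whether a patient experienced a SN event is a binary variable (yes or no". The next paragraph estimates an adjusted rate ratio (aRR) "based on a modified Poisson regression model" and adds the offset: "Logarithmic transformed values of the number of cycles will be included in the modeling as offset variables". It does not say which of the two variables is the response.

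The model is then reused:

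- RBC transfusion on or after Week 5 (4.4.2.2): also given a yes/no definition, but "the offset variables will be log-transformed values for duration of treatment (weeks) rather than cycles".
- G-CSF use (4.4.2.3): "Statistical analysis method is similar to that for SN incidence described in Section 4.4.2.1".
- Other dichotomous endpoints (4.4.3.3): "The statistical analysis approach is similar to that described for SN incidence in Section 4.4.2.1". Antibiotics, infection SAEs and lung infection SAEs take log(weeks); the rest take log(cycles).

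The major adverse hematologic event (MAHE) endpoint, which is a count, is analysed separately "using a negative binomial regression model" (4.4.2.4). For SN, 4.4.2.1 also says "Cochran-Mantel-Haenszel (CMH) weights will be used to calculate the adjusted rate difference between the two arms", with a stratified exact CMH p-value, as a check on stability. Protocol 2.2 words the SN endpoint as occurrence, and Protocol 10.3.5 plans percentages and between-group differences with no exposure adjustment.

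**The concern.** A log(cycles) offset assumes that the expected response is proportional to the number of cycles. That suits a count of event cycles. It does not suit a yes/no outcome: a patient who scores yes in Cycle 1 can score no more, yet every later cycle still enlarges the denominator. An arm treated for longer then looks better without fewer patients being affected.

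The difference in exposure could favour trilaciclib. Protocol 1.3.1 reports less discontinuation on trilaciclib than on placebo in the earlier trials. At stake are the aRR, its confidence interval and its p-value for three key secondary endpoints (SN, RBC transfusion, G-CSF use) and for the dichotomous endpoints in 4.4.3.3.

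**Working it through.** **The plan's own figure.** The documents give no numerical figure for this model. The only design calculation concerns Cycle 1 DSN, and it reproduces: 10,000 simulated trials with 35 per group and Poisson means 0.105 and 0.598 give 94.5% power against the stated 95% or so, and 70/0.88 = 79.5, hence 80 subjects. It does not involve the offset.

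**Which response?** Four features point to the yes/no variable: the section concerns an incidence, the indicator is defined immediately before the model, the model is reused under a heading for dichotomous endpoints, and the count endpoint MAHE has its own model. This is the natural reading, but it is an inference.

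**Algebra.** With treatment as the only term, a Poisson model with log link and log(cycles) offset estimates, in each arm, events divided by total cycles. For a yes/no response and equal arm sizes:

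aRR = risk ratio × (mean cycles placebo / mean cycles trilaciclib)

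Example with 18/40 affected in each arm and 5 (trilaciclib) versus 4 (placebo) cycles: (18/200)/(18/160) = 0.80. A direct fit gives the same value (p = 0.37). At 4.5 versus 4 cycles it is 0.89, and at 6 versus 4 it is 0.67. Without the offset it is 1.00 in every case.

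**No effect on risk, assumed 5 versus 4 cycles.** If each cycle carries the same risk p in both arms, occurrence over n cycles is 1 − (1 − p)^n. The offset multiplies the risk ratio by 4/5.

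| Scenario | Occurrence, 4 cycles | Occurrence, 5 cycles | Risk ratio, no offset | aRR with offset |
|---|---|---|---|---|
| p = 5% | 18.5% | 22.6% | 1.22 | 0.98 |
| p = 15% | 47.8% | 55.6% | 1.16 | 0.93 |
| p = 30% | 76.0% | 83.2% | 1.09 | 0.88 |
| Equal risk, Cycle 1 only | equal | equal | 1.00 | 0.80 |

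At 6 versus 4 cycles the last column becomes 0.95, 0.87, 0.77 and 0.67.

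**Which row is closest for SN?** In the integrated analysis, 49.6% of placebo patients had SN in Cycle 1 (SAP 2.2) and 52.9% at any time (Protocol Table 3). So 49.6/52.9 = 94% of affected placebo patients were already affected in Cycle 1, close to the last row. For trilaciclib, 6.7/11.4 = 59%.

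**Effect on the test.** Simulation used 40 per arm, 3,000 runs, cycles capped at 6 and no covariates, with equal 45% occurrence unrelated to later cycles. Rejection at the two-sided 5% level with the offset was 4.9% (mean cycles, placebo versus trilaciclib, 4 versus 4), 6.9% (4 versus 4.5), 13.8% (4 versus 5) and 27.5% (3.5 versus 5). Without the offset it was 3.9%.

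**Count as response.** With an equal constant per-cycle risk of 5% to 40% and means of 4 versus 5 cycles, modelling the number of event cycles with the offset gave ratios of 1.00 to 1.01 and rejection of 4.4% to 5.4%. If events fall only in Cycle 1, the count equals the indicator and its ratio is also about 0.80. That is a valid rate per cycle, but not a comparison of occurrence.

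**The case against.** The strongest reply is that the response may be the count. Section 4.4.2.1 defines the count first and asks for a rate ratio. In 4.4.3.3, ESA, IL-11 and TPO use have only a count of cycles defined, yet they receive the same model. If the count is meant, the offset is appropriate. This stands as an ambiguity, so a reader who infers that the SAP demonstrably fits the wrong model goes further than the text allows.

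Second, the offset does some useful work. At a low, constant per-cycle risk it errs by 2% to 7% (p = 5% to 15%), whereas dropping it errs by 16% to 22% in the other direction. This stands too: removing the offset is not neutral, because equal occurrence over more cycles can mean a lower risk per cycle.

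Third, the exposure gap is assumed. The documents give a median of 4 cycles in trilaciclib-exposed cancer patients, not split by arm. The one comparative figure, 9.0% versus 11.0% stopping any study drug because of TEAEs (Protocol 1.3.1), does not establish a gap of one cycle. First-line treatment is capped at 6 cycles. The 0.80 figure also cannot be carried to every endpoint: RBC transfusions count only from Week 5, and prophylactic G-CSF is barred in Cycle 1.

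Fourth, the CMH analysis has no offset and could reveal a discrepancy. It is planned only as a stability check, however, and leaves the aRR uncorrected.

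**Conclusion.** The concern holds as a mismatch between outcome and offset, on the natural but unstated reading that the response is yes/no. Given that reading and more cycles on trilaciclib, the direction of the lean is not in doubt. Its size is conditional: 0.98 to 0.88 at an assumed 5 versus 4 cycles with constant per-cycle risk, and 0.80 if events are confined to Cycle 1, which is close to the earlier placebo pattern for SN. With equal mean cycles there is no lean in the unadjusted ratio. The week-based offsets share the mechanism.

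A reader might infer that the key secondary results will be biased towards trilaciclib, or that the SN conclusion is in danger. The documents support neither. Cycles by arm are unknown, and the earlier SN contrast (11.4/52.9 = 0.22) is so far from 1 that a factor of 0.80 would change the estimate rather than the conclusion. The primary endpoint and its power are untouched. The point is worth settling because it affects how key secondary ratios are labelled and tested, and is cheap to correct.

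**What to change.** In SAP 4.4.2.1, 4.4.2.2, 4.4.2.3 and 4.4.3.3, name the response variable and match the offset to it, before the first unblinded analysis:

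- **Occurrence (the protocol's endpoint):** yes/no response, log link, robust variance, no offset. Call the result an adjusted risk ratio; it is then consistent with the CMH difference.
- **Exposure-adjusted rate:** number of event cycles with log(cycles), or number of events with log(weeks), using robust or negative binomial variance. Call the result a rate ratio. The SAP already derives these counts.

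Report both, state which is the main one, and show cycles and weeks on treatment by arm beside them. The cost is SAP wording and a model option, with no new data. The downside is that the risk ratio without an offset counts against the longer-treated arm when per-cycle risk is constant (1.22 to 1.09 at 5 versus 4 cycles for risks of 5% to 30%). This is why the count-based rate ratio should stand alongside it.
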